#### 10.7.6 Secondary ██████████ Endpoints

For the analysis of the secondary endpoints,

- WOMAC® VA3.1 pain subscale (WOMAC® subscale A) at Month 3
- WOMAC® VA3.1 total score over time

groups will be compared using a parametric or non-parametric ANCOVA (according to the normality of data and the homogeneity of the variances) with the following factors: baseline value and group. Repeated measures analyses will be performed on longitudinal data.

**JTA-KOA1 - Clinical Study Protocol**

JTA-KOA1-CSP

V 04

Author: EB

Date: May 10, 2017

Pg. 81/114

In each group separately, the evolution of each parameter between baseline and each time point will be described using the number of observed values, mean, standard deviation (SD) 95%-confidence intervals.

Categorical data will be presented using counts (number and number of non-missing data) and percentages.

#### 10.7.7 Safety Analysis

All safety analyses will be conducted on the SAF and tabulated by treatment group.

#### AE/SAE

AE/SAE will be coded using the MedDRA. For each AE reported, the number and percentage of patients will be tabulated based on system organ class and preferred term. Similar tabulations will be performed by severity, relationship to the study product/procedure, action taken and outcome. The number and percentage of patients who experienced an AE as defined in the pre-defined subsets of events will also be tabulated.

The frequency of AE/SAE will be compared between the groups using chi-square or Fisher's exact tests (as appropriate).

An analysis of following parameters will also be performed:

- Treatment-emergent (S)AE (occurring or worsening after treatment)
- (S)AE leading to premature withdrawal

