**Study Endpoints and Criteria for Evaluation:**

The WOMAC® VA 3.1 pain subscale scoring at baseline and subsequent assessment time points is the major efficacy criteria

Safety Endpoints

At each follow-up visit, patients will be assessed for the occurrence of any (serious) adverse events using patient open non-directive questionnaire, physical examination (including vital signs), and laboratory measurements. The safety analyses will be based on incidence evaluation of treatment emergent adverse events by preferred term and body system. Laboratory measurements will be compared to the normal laboratory ranges and to laboratory measurements obtained at Baseline Visit.

The final Study Report will be established at Month 6.

Evaluation Time Points

Safety and efficacy endpoints will be evaluated at each of the 3 follow-up visits during the 6-month follow-up period (notably at 2 weeks, 3 months and 6 months after study drug administration).

**Statistical Analysis:** Full Analysis Set (FAS) will be used for the selection of the most effective strength and for the superiority objective.

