### **3.2.4 Safety Endpoints**

From the treatment visit to the end of the study period at Month 6, patients will be systematically assessed for the potential occurrence of any adverse events (AEs) and serious adverse events (SAE), related or not to the product or the procedure, using patient open questionnaire, physical examination (including vital signs), and laboratory measurements.

The final Study Report will therefore be established at Month 6.

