## 7 SAFETY ASSESSMENTS

### 7.1 Overview of Safety Parameters and Endpoints

The safety and tolerability of investigational medicinal products will be systematically investigated throughout the whole study period. AEs will be collected and reported from the time the patient signs the informed consent until study completion. Patients will be evaluated at each visit for the potential occurrence of any AE/SAE using the following safety criteria listed in the table below. Definitions of AE and SAE are given in Section 8.1.

Table 4 below shows how the safety endpoints of this study are related to the study objectives. Assessments and measurements will be carried out at the times specified in the study Flow Chart (see Section 3.6).

*Table 4: Overview of Safety Parameters and Time Points*

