**8 SAFETY DEFINITIONS AND REPORTING REQUIREMENTS****8.1 Definitions****8.1.1 Adverse Event (AE)**

An adverse event (AE) is defined as any untoward medical occurrence in a patient or clinical investigation subject who has been administered a pharmaceutical product and/or any investigational medicinal product and which does not necessarily have a causal relationship with this treatment. An AE can therefore be any unfavourable and unintended signs (including any abnormal laboratory findings), symptoms, or disease temporally associated with the use of a medicinal product, without any judgment about causality. Adverse events will be graded with respect to intensity and classified as either serious or non-serious according to the World Health Organisation Classification.

All disease signs and symptoms experienced by the patient will be recorded on the eCRF from the time of the patient signs the ICF until completion of the final study visit.

If clinically significant worsening of the patients' physical condition is noted, the changes will be documented as AE on the AE Page of the eCRF. Clinical significance is defined as any variation in signs, symptoms, or testing that has medical relevance and may result in an alteration in medical care.

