**Table 7: Observation Period for the Occurrence of AE and SAE**

Start of Study AE/SAE Observation Period	Visit #1 (ICF signature)
End of Study AE/SAE Observation Period	6 months after treatment (Study completion)

Furthermore, any events volunteered by the patient during or between the follow-up visits, or detected through observation, physical examination (including vital signs), laboratory testing, or other clinical procedures during the observation period will be documented. Patients will be instructed that they must immediately report any AEs, complaints, or objective changes in their well-being to the Investigator or clinic personnel, regardless of the perceived relationship between the event and the investigational medicinal product.

In the event of an AE/SAE, the Investigator will immediately initiate appropriate therapy and management according to his/her medical judgment, and current good medical practice and will decide whether the patient must be withdrawn from the study or not. The patient must be followed up by additional examinations according to the medical judgment of the Investigator, until the AE/SAE and/or abnormal condition is resolved or the Investigator deems further observations or examinations are no longer medically indicated. Any medication administered for the treatment of an AE should be recorded in the patient's eCRF.

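### Section 10.7.7 applies its only named between-group adverse-event test to all events collected from consent, although the synopsis bases safety on treatment-emergent events

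*Combined protocol and SAP*

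**What the plan says.** **Basis of the analysis.** The synopsis states: "The safety analyses will be based on incidence evaluation of treatment emergent adverse events by preferred term and body system".

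**The test.** Section 10.7.7 (AE/SAE) tabulates patients for every reported event, by system organ class and preferred term, and then says: "The frequency of AE/SAE will be compared between the groups using chi-square or Fisher's exact tests (as appropriate". Nothing limits that sentence to events after the injection. The same section goes on to list treatment-emergent events, defined as occurring or worsening after treatment, among further analyses. It names no test for them. Detailed safety methodology is left to the SAP.

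**When events start to count.** Section 7.1 says: "AEs will be collected and reported from the time the patient signs the informed consent until study completion". Section 8.1.1 records signs and symptoms "from the time of the patient signs the ICF until completion of the final study visit". Table 7 and section 10.6 also start at consent. Section 3.2.4, headed as the safety endpoints, starts later: "From the treatment visit to the end of the study period at Month 6, patients will be systematically assessed for the potential occurrence".

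**Who is analysed.** Section 10.1 defines the safety set as all treated patients, and 10.7.7 uses that set.

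**The concern.** The synopsis and 10.7.7 point to different event sets for the between-group safety comparison. Someone writing the safety tables from the synopsis would test treatment-emergent events. Someone writing them from 10.7.7 would test everything recorded since consent.

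Events before the injection cannot be caused by the product. In a count of patients with at least one event, a patient who already has a screening-period event adds nothing when a new event follows the injection. The effect is to pull the arms together in the one comparison for which the plan names a test. The expected error is a missed signal, not a false one. That matters somewhat more than usual here because sections 2.3 and 8.3 say the product has not yet been given to humans.

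**Working it through.** **Step 1: do pre-injection events reach the test as worded?**
- Collection starts at consent at Visit #1 (7.1, 8.1.1, Table 7, 10.6).
- The injection is given at Visit #2, after a call to confirm participation and after randomisation (4.2). An interval therefore exists. Its length is not visible in the public text.
- The safety set (10.1) drops patients who were never treated, but keeps everything recorded for those who were.
- The test sentence in 10.7.7 has no treatment-emergent restriction.

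So the pre-injection events of treated patients are included.

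**Step 2: arm size.** The plan gives no adverse-event rates and no safety power, so there is no plan figure for this point to reproduce. The only plan figure used is the arm size in 10.9. A difference of 7 mm, SD 10.5 mm, 80% power and two-sided 5% give 36 per group by the normal approximation and 37 by the noncentral t (power 80.8%), which matches the stated 37. Adding 10% gives 37 × 1.1 = 40.7, or the stated 41. Dividing by 0.9 would give 41.1, or 42, which makes no difference here.

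**Step 3: formula.** Let r be the post-injection risk and p the pre-injection risk, with p equal across arms and independent of later events. The all-event risk is

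q = 1 − (1 − p)(1 − r),

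so the difference between two arms is q₁ − q₀ = (1 − p)(r₁ − r₀). The shrinkage is relative: the difference is multiplied by (1 − p).

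**Step 4: illustration.** All rates are assumed: r₀ = 10%, r₁ = 30%, one JTA-004 arm against the reference, 41 per arm, two-sided 5%. For p = 10%, q₀ = 1 − 0.9 × 0.9 = 19% and q₁ = 1 − 0.9 × 0.7 = 37%.

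| p (assumed) | q₀ | q₁ | Difference (points) | Chi-square power | Fisher power |
|---|---|---|---|---|---|
| 0 (treatment-emergent only) | 10.0% | 30.0% | 20.0 | 62% | 55% |
| 5% | 14.5% | 33.5% | 19.0 | 52% | 44% |
| 10% | 19.0% | 37.0% | 18.0 | 44% | 36% |
| 20% | 28.0% | 44.0% | 16.0 | 32% | 25% |

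Power falls faster than the difference because the added background also raises the variance. The sum of q(1 − q) over the two arms is 0.09 + 0.21 = 0.300 at p = 0, and 0.1539 + 0.2331 = 0.387 at p = 10%.

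With assumed risks of 20% and 50%, power is 83% (chi-square) and 77% (Fisher) at p = 0, 71% and 65% at p = 10%, and 59% and 53% at p = 20%.

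**Step 5: single preferred terms.** In the by-term tables, p is the pre-injection rate of that same term. If p were 1% (assumed), a 20-point difference would become 0.99 × 20 = 19.8 points.

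**Step 6: direction.** With no true difference (10% in both arms), Fisher's test rejects in 1.8% to 2.9% of cases for p of 0, 10% and 20%. The mixture does not create false signals.

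**The case against.** Most of the case on the other side limits the point without removing it.

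- **The treatment-emergent analysis is already planned.** This is true, and that analysis excludes pre-injection events, so it is not diluted. What stands against the plan is that 10.7.7 makes it an addition with no named test, while the synopsis makes it the basis.
- **Detail is deferred to the SAP.** The SAP may settle the matter, but the text supplied contains nothing that does. Until then the synopsis and 10.7.7 disagree.
- **The two start points are compatible.** Collecting from consent and evaluating the endpoint from treatment is ordinary practice, and 3.2.4 can be read that way. But 10.6 describes the safety assessment in similar terms with consent as its start, and no section states the distinction.
- **The definition already excludes pre-injection events.** Section 8.1.1 speaks of a patient "who has been administered a pharmaceutical product and/or any investigational medicinal product", which fits poorly with collection from consent. The wording covers any pharmaceutical product, though, and the same section records events from consent, so it cannot be relied on as an exclusion.
- **The loss is small by term, and nothing visible hangs on this test.** Both stand. A pre-injection cold does not mask a later hypotensive episode in a by-term table, and the SAE stopping rule in 8.4.3 is a judgement on events, not a test result.

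A reader might also infer that the sections disagree on when the window ends, since Visit #5 carries a window of ± 4 weeks in the table of contents. The documents do not support that. Table 7 gives the end as "6 months after treatment (Study completion", which equates the two, and the final visit, study completion and Month 6 elsewhere are other names for the same point.

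**Conclusion.** The point holds as an inconsistency about which events are tested. The synopsis names treatment-emergent events; the only between-group test named in 10.7.7 covers all events, including those of treated patients before injection. That comparison is attenuated by the factor (1 − p).

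The size is unknown. The documents give no pre-injection event rate, and every rate in the illustration is an assumption, as are independence and an equal p across arms. For a count of patients with any event, the loss could be material: at 10% against 30%, chi-square power drops by 10 to 30 percentage points for p from 5% to 20%. For individual preferred terms it is likely to be slight.

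A reader might go further and conclude that the plan conceals harm. It does not. The treatment-emergent results are to be produced alongside the all-event results and are free of this dilution. This is a modest correction, worth making because a better rule is already defined in the same section.

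**What to change.** - **Section 10.7.7:** state that the between-group tables and the chi-square or Fisher tests use treatment-emergent events, by the definition the section already gives (onset or worsening after the injection). List pre-injection events separately, without a test.
- **Sections 3.2.4 and 10.6:** state in both that events are collected from consent and that the safety endpoint is evaluated from the injection. This removes the difference in start points without changing collection.
- **SAP:** carry the same rule forward.

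The cost is a few sentences. The treatment-emergent classification is already planned, so no data, visit or procedure is added.

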#### Other safety variables

**JTA-KOA1 - Clinical Study Protocol**

JTA-KOA1-CSP	V 04	Author: EB	Date: May 10, 2017	Pg. 82/114
--------------	------	------------	--------------------	------------

Standard summary statistics of laboratory values and shift tables presenting incidence of laboratory abnormalities will also be provided by treatment group. The frequency of normal/abnormal examination will be tabulated for each time point and each treatment group.

Detailed statistical methodology for the safety analyses will be provided in the SAP.

### 10.8 Randomisation

Patients will be randomised in one of the three JTA-004 groups or in the reference group according to a 1:1:1:1 ratio using IWRS.

### 10.9 Sample Size Estimation

The sample size calculation for the superiority trial for the primary endpoint – change in WOMAC® VA3.1 pain subscale from baseline to Month 6 - is based the following assumptions:

- The mean pain difference of patients treated with the JTA-004 and those treated with the reference treatment is assumed to be -7 mm (i.e. the mean JTA-004 treatment is 7 mm better than the reference). The absolute mean difference is set to 7 mm which is below the accepted MCID of the WOMAC® VA3.1 pain subscale, which is 10 mm (Ehrich *et al.*, 2000; Bellamy *et al.*, 2001);
- The standard deviation of the mean pain difference between the two treatments, estimated from the Borrás-Verdera *et al.*, 2012 and Pavelka and Uebelhart., 2011 data, are in the range of 4.7 to 6.6 mm for sample sizes between 48 and 24, respectively. To ensure maximal power, a standard deviation value of 10.5 was used for sample size estimation.);

Under the scenario of a mean between group difference of -7 mm (i.e., JTA-004 is better than control by a mean of 7 mm) with a standard deviation of 10.5 mm, thirty-seven (37) patients per group are required for analysis, reaching a power of 80% to test for superiority, keeping the type I error at 0.05 (two-sided). This would allow collecting enough efficacy data per group while avoiding exposing too many patients.

The level of drop-out is estimated to 10%. Thus 41 patients per group have to be included.

As recruitment will continue in all 4 treatment groups until the final analysis, the maximum total number of included patients will be 164 (4 x 41).

JTA-KOA1 - Clinical Study Protocol

JTA-KOA1-CSP	V 04	Author: EB	Date: May 10, 2017	Pg. 84/114
--------------	------	------------	--------------------	------------

[REDACTED]

[REDACTED]

[REDACTED]

[REDACTED]

[REDACTED]

[REDACTED]

[REDACTED]

[REDACTED]

[REDACTED]

[REDACTED]

[REDACTED]

[REDACTED]

[REDACTED]

[REDACTED]

[REDACTED]

[REDACTED]

[REDACTED]

[REDACTED]

[REDACTED]

[REDACTED]

[REDACTED]

[REDACTED]

[REDACTED]

[REDACTED]

[REDACTED]

[REDACTED]

[REDACTED]

[REDACTED]

[REDACTED]

[REDACTED]

JTA-KOA1 - Clinical Study Protocol

JTA-KOA1-CSP	V 04	Author: EB	Date: May 10, 2017	Pg. 85/114
--------------	------	------------	--------------------	------------

[REDACTED]

[REDACTED]

[REDACTED]

[REDACTED]

[REDACTED]

[REDACTED]

[REDACTED]

[REDACTED]

[REDACTED]

[REDACTED]

[REDACTED]

[REDACTED]

[REDACTED]

[REDACTED]

[REDACTED]

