**JTA- KOA1 - Clinical Study Protocol**

JTA-KOA1-CSP

V 04

Author: EB

Date: May 10, 2017

Pg. 8/114

*Primary Endpoint*

The primary endpoint is the change between baseline and Month 6 of the Western Ontario and McMaster Universities (WOMAC® VA3.1 pain subscale (subscale A).

Primary study objectives are (i) the selection of the best JTA-004 strength and (ii) superiority assessment of the best JTA-004 strength efficacy to the reference or (iii) stop the trial at interim analysis for futility. They will be determined as follow:

- For selection of best JTA-004 strength, by comparing the different JTA-004 strengths to the reference with respect to the WOMAC® VA3.1 pain subscale score (mean differences between baseline and Month 3)
- For superiority assessment, by comparing the best JTA-004 strength and reference on the mean differences in WOMAC® VA3.1 pain subscale score between baseline and Month 6, assuming a mean between group difference of 7 mm in favor of the best JTA-004 strength (i.e., difference JTA-004 minus Reference of -7 mm) with a standard deviation of 10 mm.

The following hypothesis is stated to show superiority of JTA-004 to Reference:

- H0: The difference in the mean change from baseline at Month 6 between JTA-004 and Reference is superior or equal to 0.
- H1: The difference in the mean change from baseline at Month 6 between JTA-004 and Reference is inferior to 0.

The secondary efficacy endpoints are:

- WOMAC® VA3.1 pain subscale (WOMAC® subscale A) at Month 3
- WOMAC® VA3.1 total score over the time

*Safety Analysis*

All safety analyses will be conducted on the safety population and tabulated by treatment group.

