For these reasons, among the several commercially available HA preparations, Synvisc-one® was selected as reference in this clinical trial. Indeed, Synvisc-One® is an approved and well-established treatment of knee OA in Europe and USA. Three clinical trials have shown that Synvisc-One® is safe and effective by providing statistically significant and clinically relevant pain relief in patients suffering from knee OA. The first study (Conrozier et al., 2009) demonstrated that a single 6 ml intra-articular injection of Synvisc-One® is as safe and effective that multiple injection (2 ml, three time, one week apart) in providing statically significant, clinically relevant pain relief, as measured by WOMAC® A pain scores at 24 weeks. A change from baseline at 24 weeks of -34.9 mm (corresponding to a mean percentage change in pain from baseline of 54.7 %). The second study (Chevalier et al., 2010), a controlled randomised, multicenter, double-blind study, compares a single (6 ml) IA injection of Synvisc-One® to a placebo (PBS). This study demonstrated that a single 6 ml intra-articular injection of Synvisc-One® provides statically significant, clinically relevant pain relief, as measured by WOMAC® A pain scores over 26 weeks, with a modest difference compared with placebo (-3,0 mm, SEM 1,52, p = 0.047). An estimated change from baseline over 26 weeks of -21 mm (corresponding to a mean percentage change in pain from baseline of 36 %) is observed for Synvisc-One® versus an estimated change from baseline of -17,25 mm (corresponding to a mean percentage change in pain from baseline of 29 %) observed for placebo demonstrating that Synvisc-One® is reliably superior to placebo. The last study (Drieser et al., 2015) compared a high molecular weight hyaluronan (Ostenil®Plus) to Synvisc-One®. In this randomised, double-blind study, an estimated change from baseline after 26 weeks of -34.3 mm (corresponding to a mean percentage change in pain from baseline of 58.9 %) is observed for Ostenil®Plus versus an estimated change from baseline of -36.2 mm (corresponding to a mean percentage change in pain from baseline of 62.5 %) observed for Synvisc-One® demonstrating that both treatments provide statistically significant and clinically relevant pain relief.

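### Section 10.9 rests its patient SD of 10.5 mm on figures that read more like standard errors; if they are, power for 7 mm at 37 per group, before any interim re-estimation, is about 45% or 25% rather than 80%

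*Combined protocol and SAP*

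**What the plan says.** Section 10.9 (Sample Size Estimation) sizes the Month 6 superiority comparison for a 7 mm advantage over the reference. It introduces its evidence on variability as "The standard deviation of the mean pain difference between the two treatments", taken from two published trials, and reports values that "are in the range of 4.7 to 6.6 mm for sample sizes between 48 and 24, respectively". It continues: "To ensure maximal power, a standard deviation value of 10.5 was used for sample size estimation". From this it concludes that "thirty-seven (37) patients per group are required for analysis, reaching a power of 80% to test for superiority", at a two-sided type I error of 0.05. With 10% drop-out this becomes 41 per group and 164 in total.

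The same section notes that 7 mm is a difference "which is below the accepted MCID of the WOMAC® VA3.1 pain subscale, which is 10 mm".

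The synopsis (Primary Endpoint) describes the same comparison and the same 7 mm, but "with a standard deviation of 10 mm".

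**The concern.** The calculation needs the between-patient SD of the change score. The evidence offered is described as the SD of a mean difference, and each value comes with a sample size. Both features belong to a standard error. Section 10.9 does not say which kind of quantity it is, or whether 48 and 24 are trial totals or group sizes.

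Nor does it show how 10.5 mm follows from 4.7 and 6.6 mm. The stated motive, maximal power, is not a derivation: at a fixed sample size, a larger assumed SD lowers the calculated power.

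The stated 80% power of the confirmatory test depends on this one input. If the published values are patient SDs, 10.5 mm is generous. If they are standard errors, 10.5 mm is well below the patient SD they imply. A reader cannot tell from the text which applies.

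**Working it through.** **Inputs.** From 10.9: difference 7 mm, SD 10.5 mm, two-sided 0.05, 80% power, 37 per group, 10% drop-out, and source values of 4.7 mm (n = 48) and 6.6 mm (n = 24). From the synopsis: SD 10 mm. From 10.8: equal allocation. Assumption: an unadjusted two-sample t-test, because the visible text of 10.7.5 names no model for the primary endpoint.

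**1. The plan's own figure.** The standard error of the difference is SD × √(2/n) = 10.5 × √(2/37) = 2.44 mm. The noncentrality is 7/2.44 = 2.87 on 72 degrees of freedom, which gives power 80.8%. With 36 per group it is 79.7%, so 37 is the smallest adequate number. Then 37/0.9 = 41.1, stated as 41, and 4 × 41 = 164. The arithmetic holds, and it shows that 10.5 mm is used as a between-patient SD.

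**2. The synopsis SD.** With 10 mm, 34 per group are needed (power 81.2%; just under 80% at 33). At 37 per group, power would be 84.4%.

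**3. Do the source values behave like standard errors?** A standard error falls with 1/√n, so the expected ratio is √(48/24) = 1.414. The observed ratio is 6.6/4.7 = 1.404. Allowing for rounding, it lies between 6.55/4.75 = 1.379 and 6.65/4.65 = 1.430, which contains 1.414.

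For a rough weight, suppose the two values come from independent samples of 48 and 24 that share one true patient SD. If the values are patient SDs, the chance of a ratio in that window is about 1.2% (F distribution, 23 and 47 degrees of freedom). If they are standard errors, it is about 8.0%. The ratio therefore favours standard errors by about 8.0/1.2, or between 6 and 7 to 1, under those assumptions. That is support, not proof.

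**4. Conversion to a patient SD, if they are standard errors of a difference.**
- 48 and 24 as totals, SE = SD × √(4/n): 4.7 × √12 = 16.3 mm and 6.6 × √6 = 16.2 mm.
- 48 and 24 per group, SE = SD × √(2/n): 4.7 × √24 = 23.0 mm and 6.6 × √12 = 22.9 mm.

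Under either convention the two values give nearly the same patient SD.

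**5. Consequences at 37 per group for 7 mm, before any re-estimation.** The difference detectable with 80% power is proportional to the SD. At 10.5 mm it is 6.93 mm, so the factor is 6.93/10.5 = 0.66.

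| Reading | Patient SD (mm) | Power | Detectable with 80% power (mm) | Per group for 80% |
|---|---|---|---|---|
| Source values are patient SDs | 4.7 | >99.9% | 3.1 | 9 |
| Source values are patient SDs | 6.6 | 99.4% | 4.4 | 15 |
| Synopsis | 10 | 84.4% | 6.6 | 34 |
| Section 10.9 as planned | 10.5 | 80.8% | 6.9 | 37 |
| Standard errors, n as totals | 16.2 | 45% | 10.7 | 86 |
| Standard errors, n per group | 23 | 25% | 15.2 | 171 |

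On both standard-error readings the detectable difference exceeds the 10 mm MCID quoted in 10.9.

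**The case against.** The strongest defence is the literal one. The text says standard deviation, 10.5 mm exceeds both cited values, and 37 per group follows correctly from it. On that reading the planners rounded up generously, and only the wording needs attention. The standard-error reading rests on two numbers from publications not available here, and 10.9 does not say which value came from which trial. All of this stands, and it is why the point is put as a conditional. It does not remove the gap: on the literal reading too, 10.5 mm is not derived from anything shown.

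A second defence is that sample size will be reassessed at the interim (Synopsis; section 3.1), so 37 is provisional. That also stands, and the powers above are for the position before that step. The reassessment rule cannot be read in the public copy. What is visible is mixed: the reassessment uses three-month data while the SD concerns Month 6, and 10.9 calls 164 a maximum while the synopsis allows adjustment. Power after re-estimation is not judged in either direction.

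Four stronger readings are tempting, and the documents do not support them.
- A reader might infer that the trial has 45% or 25% power. That follows only if the values are standard errors, and this is not established.
- A reader might infer that the protocol contains no derivation anywhere. Sections 10.10 to 10.12 cannot be read in the public copy, so the point is limited to the visible text of 10.9 and the synopsis.
- A reader might turn to the placebo arm in section 5.4 ("versus an estimated change from baseline of -17,25 mm") and argue that an SD of 4.7 to 6.6 mm would leave almost no placebo patient unimproved. The documents do not say how many placebo patients failed to improve, and that figure is an estimate over 26 weeks, so there is no benchmark.
- A reader might expect baseline adjustment to restore the power. The ANCOVA in 10.7.6 is specified for secondary endpoints, and no baseline correlation is given from which to compute a gain.

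**Conclusion.** The point holds as a problem with the planning input, not with the arithmetic. The visible support for 10.5 mm is ambiguous, and its label, attached sample sizes and scaling lean towards standard errors of a between-group difference. The stated 80% is right only if the patient SD of the Month 6 change is about 10.5 mm. The cited values, read either way, point elsewhere: power above 99% if they are patient SDs, about 45% (SD 16.2 mm) or 25% (SD 23 mm) if they are standard errors.

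These figures assume 37 evaluable patients per group, a 7 mm difference, two-sided 0.05, an unadjusted t-test and no change at the interim. Confidence in the standard-error reading is moderate. Confidence that 10.9 leaves the question open, and that the synopsis and 10.9 disagree on the SD, is high. It should be fixed, because the planned power of the confirmatory comparison depends on it.

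**What to change.** In section 10.9:
1. Check the two cited publications. State whether 4.7 and 6.6 mm are standard errors of the between-group difference or patient SDs, and whether 48 and 24 are totals or group sizes.
2. Convert them to a patient SD of the Month 6 change, and put that derivation in place of the appeal to maximal power. Suggested wording: *The published values are [standard errors of the difference / patient SDs] with n [in total / per group], corresponding to a patient SD of [x] mm. With 37 evaluable patients per group and two-sided 0.05, power for 7 mm is [y]% and the difference detectable with 80% power is [z] mm, before any interim re-estimation.*
3. Use one SD in the synopsis and in 10.9.

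The cost is a check of two papers already cited and a few sentences of text. No added patients are proposed; any change in sample size is left to the reassessment already planned. The downside is that the stated power may become less favourable.
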